### **Suspected Unexpected Serious Adverse Reaction (SUSAR)**

A Suspected Unexpected Serious Adverse Reaction (SUSAR) is defined as a SAR that has not been previously documented in the product literature, the nature and severity not being consistent with the product information.

## **12.3. Recording and reporting Serious Adverse Events**

In the case of a SAE (SAR/SUSAR) the Investigator must **immediately** on becoming aware of the event:

- ❑ **Complete a ‘Serious Adverse Event Form’**. This should contain all of the information known at the time of the report
- ❑ **Fax** within 24 hours of becoming aware of the event the signed and dated ‘Serious Adverse Event Form’ to the **TEAM** study office at the CRCTU, Birmingham: **UK [contact]**

- ❑ **Telephone** (on day of awareness) the *TEAM* study office at the CRCTU, Birmingham in the case of death or life-threatening events: ☎: **[name] (Mon-Fri, 9am –5pm)**
- ❑ In addition, send by post the original copy of the SAE form and ensure that the reporting clinician has signed/dated it.

The *TEAM* study office will inform Pfizer UK who will notify the relevant regulatory authorities (MHRA/IMB). The *TEAM* study office (with the consultation of the Chief Investigator) will inform the Multicentre Research Ethics Committee (MREC), each centre should inform their Local Research Ethics Committee (LREC) of SAEs. The annual report (detailed in section 17 - Ethical Requirements) contains details of SAEs; this report will be sent to MREC and participating centres, which should then send this report to their LREC as soon possible.

#### **12.4. Follow-up of AEs/SAEs**

All AEs will be recorded on the CRFs until 30 days after the last treatment dose on study or until the start of other anti-cancer treatment, whichever occurs first. Additionally, all AEs deemed possibly related to the trial medication (exemestane or tamoxifen) will be followed until resolution, or the Investigator assesses them to be chronic or stable, or initiation of other anti-cancer therapy, whichever occurs first.

In the case of a SAE, the subject must be followed-up until clinical recovery is complete and laboratory results have returned to normal, or until disease has stabilised. Follow-up may continue after completion of protocol treatment if necessary. Follow-up information can be added to the original (or copies) of the initial SAE form. Extra annotated information and/or copies of test results may be provided separately.

#### **13. DRUG SUPPLIES**

Tamoxifen prescribing should be initiated by the Investigator, and continued supply arranged according to normal local practice.

Exemestane treatment should be initiated by the Investigator, with drug supply for the entire treatment period arranged through the participating hospital pharmacy. In the first year of treatment the patient will receive three monthly supplies of exemestane, corresponding to the frequency of follow-up visits required. Thereafter the patient will be given up to six months supply of exemestane at a time. The medication will be commercial stock in standard packaging. The pharmacist should label the drugs on receipt.

#### **14. DETERMINATION OF EFFICACY**

Patients on both treatment arms are followed-up at specified intervals and evaluated for evidence of relapse. Required evaluations at each time-point are specified in Section 10.3 of this protocol.

##### **14.1. Disease-Free Survival (DFS)**

Disease-Free Survival (DFS) is defined as the time from randomization to the earliest recorded documentation of local/regional or distant recurrence of breast cancer, new 2nd primary (contralateral) invasive breast cancer or death from any cause. Patients who have not had any such event (relapse or death) at the time of data analysis will be censored at 2.75 years for the first co-primary endpoint and at the last date they were known to be event-free for the 2nd co-primary endpoint and the secondary endpoints. Kaplan-Meier estimates of the survival curves for each treatment arm (including medians and 95% confidence intervals) as well as the result of the log-rank test will be presented.

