## **6.5. Registration of relapse and death**

In the case of any relapse the adjuvant treatment must be stopped, and this is registered as an event. Full details of relapse should be recorded on the trial Case Report Form (CRF) and returned to the CRCTU. A summary of treatment offered at relapse will also be requested. Any malignant contralateral breast cancer will be registered as a second primary, and relapse with supraclavicular disease will be registered as distant relapse, unless otherwise specifically indicated.

‘Breast cancer’ deaths will be all deaths with breast cancer specified as a cause of death and deaths from any cause following a distant relapse.

All patients will be evaluated for endpoints in the treatment arm to which they were randomised, irrespective of the treatment they actually received. No patient will be removed from the analyses, irrespective of whether she is found to have violated an eligibility criterion after randomisation or to have been withdrawn from trial medication prematurely. Thus analysis will be by “intention-to-treat”, including all patients randomised.

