## **11. WITHDRAWAL**

Patients have the right to withdraw from the study at any time for any reason. The Investigator also has the right to withdraw patients from the study. Full details of the reasons for withdrawal should be recorded on the CRF if clinician initiated, otherwise a simple statement reflecting patient preference will suffice. Withdrawn patients should continue to be followed-up in accordance with the protocol with their permission.

A patient will be withdrawn from the trial if any of the following occur:

- Relapse (appearance of metastatic cancer)
- The patient, in the opinion of the treating physician, is unable to tolerate the toxicity resulting from the hormonal treatment
- Non-adherence with protocol/treatment
- Refusal and/or reservations of the patient to continue treatment or withdrawal of consent.
- Patient lost to follow-up

The date and reason for discontinuation must be recorded on the CRF. Every effort should be made to complete the appropriate assessments.

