## 14.2. Overall Survival (OS)

OS is defined as the time from first trial drug administration to date of death. In the absence of confirmation of death, survival time will be censored to last date of follow-up.

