### 15.2. Hypothesis and sample size

In the amended protocol (27th October 2004), patients in the tamoxifen arm are assumed to switch to exemestane after 2¾ years (range from 2½ -3 years) of treatment with tamoxifen. The main goals of this study are to compare the DFS among patients who received either exemestane 25 mg or tamoxifen for 2.5- 3 years followed by 2.5- 2 years of exemestane for 2.75 years (i.e. 33 months), and for 5 years. Overall survival and DFS at 10 years will be evaluated. The safety for both arms at 2.75 years and 5 years will also be assessed.

The ATAC paper provided updated information comparing tamoxifen and anastrozole. The 3-year DFS rate was estimated to be approximately 90% for the tamoxifen arm (i.e., Arm B before switch). If the hazard ratio of DFS is assumed to be 1.28 between the two treatment arms (Arm B / Arm A), **723 events** will achieve 87% power to detect the corresponding difference in DFS with a two-sided significance level of 0.0298. Assuming constant exponential rates in both groups with a hazard ratio of 1.28), **9300 patients (4650 in each group) are sufficient in order to observe these 723 events after each subject is followed for 2.75 years.** The Independent Data Monitoring Committee, as part of their evaluation of the progress of the trial, will review an interim analysis at the time 50% of the events are reported for the first co-primary endpoint, at or before 2.75 years from the time of randomization.

The entire TEAM trial will accrue a total of 9300 patients in order to observe 723 DFS events at 2.75 years (33 months). UK will contribute approximately 1200 patients.

**Timing of the first primary analysis of DFS:** approximately 2¾ years after the last patient has been enrolled when there will be at least 723 events. Based on this, the following hypotheses are stated:

**A:** under the null-hypothesis ( $H_0$ ) if there is no difference between the two treatments, assuming the 3-year DFS is 90%, then: treatment arm A (tamoxifen) and treatment arm B (exemestane) will show a 3 years DFS of 90%.

**B:** under the alternative hypothesis ( $H_1$ ) the HR is 1.28 for the first 2¾ years and hence ( $H_0$ ) is rejected.

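### Section 14.1 censors every event-free patient at exactly 2.75 years for the first co-primary endpoint, so patients lost earlier are counted as disease-free over time nobody observed

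*Protocol*

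**What the plan says.** Protocol section 14.1 sets the DFS censoring rule for "Patients who have not had any such event (relapse or death) at the time of data analysis". Such patients "will be censored at 2.75 years for the first co-primary endpoint and at the last date they were known to be event-free". The sentence then ties this last-date rule to the second co-primary and the secondary endpoints only. One sentence therefore gives two rules. The first co-primary endpoint gets a fixed time, and every other DFS analysis gets the last event-free date. Nothing covers a patient whose follow-up stopped before 2.75 years.

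Other sections bear on this:

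- Section 14.2, on overall survival, uses the usual rule: without a confirmed death, "survival time will be censored to last date of follow-up".
- Section 11 lists "Patient lost to follow-up" as a reason for withdrawal and adds that "Withdrawn patients should continue to be followed-up in accordance with the protocol with their permission". Section 6.6 likewise has a withdrawing patient asked whether her data may go on being used.
- Section 6.5 makes the analysis intention-to-treat, "including all patients randomised".
- Section 15.2 times the first primary analysis at "approximately 2¾ years after the last patient has been enrolled when there will be at least 723 events".

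Sections 15.2, 15.4.1 and 15.6 contain no other censoring rule.

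**The concern.** A patient who leaves follow-up early can no longer have a recorded event. If her time is set to 2.75 years, she stays in every later risk set as though she were being watched and were well. Both Kaplan-Meier curves then sit too high.

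For the log-rank comparison, what matters is whether this happens equally in the two arms. The trial is open label, so loss could differ by arm. If it does, the arm that loses more patients appears to have fewer failures, and the primary test can reject a true null too often. The same error can also add to or take away from a real effect.

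The interim analysis at half the events raises a related problem. Many patients will not yet have been followed for 2.75 years, and the wording would credit them with that time as well.

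**Working it through.** **Inputs from the protocol.** Tamoxifen DFS of 90% at 3 years, hazard ratio 1.28 (tamoxifen over exemestane), constant hazards, 4650 patients per arm, 723 events, two-sided level 0.0298 and 87% power (all section 15.2); log-rank test (section 15.4.1). **Assumed, because the protocol gives none:** the proportion lost by 2.75 years, with exponential loss times independent of outcome.

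**1. The plan's own figures.** The critical value for 0.0298 two-sided is z = 2.173. Power = Φ(½√723 × ln 1.28 − 2.173) = Φ(3.319 − 2.173) = 0.874, against the stated 87%. For 87% power, Freedman's formula gives 722 events and Schoenfeld's 715. The hazards are −ln(0.90)/3 = 0.03512 per year on tamoxifen and 0.03512/1.28 = 0.02744 on exemestane. Failure by 2.75 years is 1 − exp(−2.75λ), which gives 9.21% and 7.27%, a difference of 1.94 points. Expected events without loss are 4650 × (0.0921 + 0.0727) ≈ 766, so 9300 patients suffice. The design reproduces.

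**2. What the rule does to one arm.** Let d be the proportion lost and c = −ln(1 − d)/2.75 the loss rate. Under the rule as written nobody is censored before 2.75 years, so the estimated failure probability is simply the share of patients with an observed event:

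P(d) = λ/(λ + c) × [1 − exp(−2.75(λ + c))]

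For tamoxifen with d = 5%, c = 0.01865 and P = 0.6531 × 0.1375 = 8.98%. That is 0.23 points below 9.21%. With d = 10%, P = 8.75%, which is 0.46 points below.

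**3. Equal loss in both arms.**

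| Loss per arm | Tamoxifen failure | Exemestane failure | Difference | Apparent HR | Patients lost event-free | Person-years credited but unobserved |
|---|---|---|---|---|---|---|
| 0% | 9.21% | 7.27% | 1.94 | 1.28 | 0 | 0 |
| 5% | 8.98% | 7.09% | 1.89 | 1.28 | about 446 | about 630 |
| 10% | 8.75% | 6.90% | 1.84 | 1.28 | about 890 | about 1270 |

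The levels move, but the comparison hardly does.

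**4. Unequal loss with no true effect.** Give both arms the tamoxifen hazard. The apparent hazard ratio is ln(1 − P₁)/ln(1 − P₂), and the shift in the test statistic is ½√D × ln(HR), where D = 4650(P₁ + P₂). Type I error is the probability of falling beyond ±2.173 after that shift.

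| Loss, arm 1 vs arm 2 | P₁, P₂ | Spurious HR | D | Shift | Type I error |
|---|---|---|---|---|---|
| 5% vs 5% | 8.98%, 8.98% | 1.000 | 835 | 0 | 2.98% |
| 5% vs 6% | 8.98%, 8.93% | 1.005 | 833 | 0.08 | 3.03% |
| 5% vs 10% | 8.98%, 8.75% | 1.028 | 824 | 0.39 | 4.3% |
| 5% vs 15% | 8.98%, 8.51% | 1.058 | 813 | 0.80 | 8.7% |

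A log-rank simulation (3000 runs per scenario, Monte Carlo standard error about 0.3 points near the nominal level) gave 3.7% to 4.2% for a 5%/10% split, depending on which arm lost more, and 8.7% for 5%/15%. With censoring at the earlier of the last event-free date and 2.75 years, the same simulated loss scenarios gave 2.5% to 3.0%.

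**5. Unequal loss with a true HR of 1.28.** With 5% lost on tamoxifen and 10% on exemestane, the apparent HR is about 1.31 and simulated power about 0.94. With the split reversed, they are about 1.25 and 0.79. Under the corrected rule power stays at about 0.87 to 0.88.

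**The case against.** The strongest reply is that a plain administrative cut-off was meant. The first primary analysis comes about 2¾ years after the last enrolment, so nearly every event-free patient will have reached 2.75 years, and for her the sentence is right. The protocol also works against loss. Follow-up continues after treatment stops (sections 6.6, 10.3 and 10.4), missed visits are to be chased, and patients transferred elsewhere are followed annually through the GP or other hospital. No loss rate is given, so gaps of 5 or 10 points between arms have no source in the protocol. A one-point gap does almost nothing, and equal loss leaves the test alone.

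Most of this stands, and it limits the size of the problem. It does not rescue the wording. The sentence contrasts the two rules and assigns the last-date rule to the other endpoints, so that rule cannot be read into the first co-primary. Detailed censoring rules are often left to an analysis plan, but this one is already stated, and a later plan could correct it only by departing from it.

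A reader might go further. Because the sentence covers only patients with no event when the data are analysed, one might infer that a first event in, say, year 4 would count in the first co-primary. The protocol does not support that. Sections 5, 15.2, 15.4.1 and 15.6 all tie this endpoint to 2.75 years, and section 15.4.1 places it before the switch. Section 14.1 is merely silent on late events, so no count of extra events should be attached to them.

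**Conclusion.** The concern holds as an error in a stated rule. Applied as written, section 14.1 counts unobserved time as disease-free in the first co-primary analysis for anyone lost or withdrawn before 2.75 years. At the interim analysis it does so for anyone not yet followed that long. Recruitment dates should be balanced by randomisation, so the interim effect should fall mainly on the level of the curves, much as equal loss does.

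The size depends on loss that the protocol does not quantify. Low or balanced loss produces slightly optimistic curves and no material change in the hazard ratio or type I error. Differential loss biases the test towards the arm with more loss, negligibly for a one-point gap and materially for gaps of 5 to 10 points. It would be wrong to infer that the primary test is biased whatever the loss pattern, or that the sample size is undermined: 723 events, 87% power and 9300 patients are unaffected.

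These figures assume constant hazards and loss unrelated to prognosis. If loss is related to prognosis, the corrected rule does not remove that bias either.

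**What to change.** Reword the censoring sentence in section 14.1 so that, for the first co-primary endpoint, a patient without an event is censored at the earlier of the last date she was known to be event-free and 2.75 years from randomisation. Add that a patient whose first event comes after 2.75 years is censored at 2.75 years. This makes section 14.1 agree with the endpoint as described in sections 5, 15.2, 15.4.1 and 15.6. Apply the same rule at the interim analysis.

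The cost is one sentence and the matching line of analysis code. The last event-free date is already needed for the second co-primary endpoint, so no new data are required, and the sample size and significance levels do not change. Reporting loss before 2.75 years by arm would show whether the point mattered in practice.

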## 14.2. Overall Survival (OS)

OS is defined as the time from first trial drug administration to date of death. In the absence of confirmation of death, survival time will be censored to last date of follow-up.

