###### Secondary Objectives

- DFS at 10 years
- Overall Survival (OS)
- The relative safety profiles
- Time from randomisation to new primary breast cancer in postmenopausal women treated with 5 years of exemestane versus tamoxifen therapy for 2.5- 3 years followed by 2.5- 2 years of exemestane.
- Differences in outcome based on pathological subgroups will also be assessed for specified participating centres/countries.
- In the first year of treatment Quality of Life (QOL) assessments in each treatment group will be made.

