### 15.4. Efficacy analysis

#### 15.4.1 First co-primary efficacy analysis

The first co-primary efficacy endpoint will be the DFS at 2.75 years post-treatment (before tamoxifen arm switching to exemestane), as estimated from the Kaplan-Meier curves for each

treatment arm. The difference in DFS will be assessed using the log-rank test at the 5% significance level, with a 90% power to detect absolute differences of 2%-3%.

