#### **15.4.2 Second co-primary efficacy analysis**

The second co-primary efficacy endpoint will be DFS at 5 years post-treatment as a point estimate obtained from the Kaplan-Meier survival estimates of the two treatment arms. The difference in 5-years DFS between the treatment arms will be reported, along with its standard error (SE) and an associated 95% confidence interval. . In addition, patients will be followed up for a minimum of 10 years and long term outcomes will be reported.

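### Overall survival is timed from the first drug dose, not from randomisation, so it is undefined for never-dosed patients and contradicts the protocol's intention-to-treat rule

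*Protocol*

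**What the plan says.** Protocol section 14.2 defines the endpoint in one sentence: "OS is defined as the time from first trial drug administration to date of death". The only other sentence in that section concerns the end of observation: "In the absence of confirmation of death, survival time will be censored to last date of follow-up". Neither gives a start date for a woman who is randomised and takes no trial drug.

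Section 6.5 sets the analysis rule for endpoints: "All patients will be evaluated for endpoints in the treatment arm to which they were randomised, irrespective of the treatment they actually received". It adds that nobody is taken out of the analyses, whether for an eligibility violation or for stopping medication early, and that the analysis is by intention to treat in everyone randomised. Section 15.4.3 makes OS at 5 and 10 years a secondary efficacy endpoint, so this rule covers it.

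The other time-to-event endpoints start at randomisation. In section 14.1, DFS "is defined as the time from randomization to the earliest recorded documentation" of an event. In section 5, a secondary objective is "Time from randomisation to new primary breast cancer in postmenopausal women".

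The analysis sections word the DFS time points differently. Section 15.4.1 reads "The first co-primary efficacy endpoint will be the DFS at 2.75 years post-treatment" and section 15.4.2 reads "The second co-primary efficacy endpoint will be DFS at 5 years post-treatment as a point estimate".

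**The concern.** A survival time needs a start date. Under section 14.2 that date does not exist for a patient who never starts, so an analyst applying the definition literally has no OS time for her and would have to leave her out. Section 6.5 says she must stay in. Both cannot be followed.

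The trial is open label, so patient and investigator know the allocation before the first dose. If the decision not to start depended on the allocated drug and on prognosis, leaving these women out could bias the OS comparison in a direction that the protocol gives no means of checking. The result would be a treated-patients comparison reported as intention to treat.

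The two clocks also conflict. Death from any cause is a DFS event, so OS should never be shorter than DFS. With a later origin for OS, a woman who dies without recurrence has an OS time shorter than her DFS time by the gap between randomisation and first dose.

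**Working it through.** **1. The plan's own figure.** The only powered quantity is the first co-primary DFS test in section 15.2: 723 events, hazard ratio 1.28, two-sided level 0.0298 (z = 2.173), stated power 87%.

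- Schoenfeld: power = Φ(√723 × ln(1.28) / 2 − 2.173) = Φ(3.319 − 2.173) = 87.4%.
- Freedman: power = Φ(√723 × 0.28/2.28 − 2.173) = Φ(3.302 − 2.173) = 87.1%.

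The figure reproduces. It concerns DFS timed from randomisation and does not change with the OS origin. The protocol states no power, event target or significance level for OS.

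**2. The texts side by side.**

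| Item | Section | Origin or population |
|---|---|---|
| OS | 14.2 | first dose; no rule for a patient without one |
| DFS | 5 and 14.1 | randomisation |
| New primary breast cancer | 5 | randomisation |
| Endpoint analyses | 6.5 | everyone randomised, by allocated arm |
| Safety analyses | 15.5 | randomised and dosed at least once |

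OS is the exception among the time-to-event endpoints. Section 15.5 shows that the protocol itself separates randomised from dosed patients, so it allows for women in the first group who are not in the second. No other section redefines OS or supplies a substitute start date.

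**3. Patients with no OS time.** Number = 9300 (section 15.2) × never-started rate. The protocol gives no such rate, so the rates below are assumptions.

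| Assumed rate | Patients |
|---|---|
| 0.25% | 23 |
| 0.5% | 47 |
| 1% | 93 |
| 2% | 186 |
| 3% | 279 |

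**4. Shift for treated patients.** Section 6.1 requires treatment to start within 5 working days of registration. Taking registration as the day of randomisation, this is about 7 calendar days.

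- Share of 5 years: 7 / (5 × 365.25) = 0.4%.
- Share of 10 years: 7 / (10 × 365.25) = 0.2%.

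**5. Deaths before the first dose.** Expected number = 9300 × [1 − (1 − m)^(7/365.25)], where m is annual mortality and every patient is taken to wait the full 7 days. The protocol gives no mortality rate; m of 1% to 3% is assumed.

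- m = 1%: 1.8 deaths.
- m = 2%: 3.6 deaths.
- m = 3%: 5.4 deaths.

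Each such death is a DFS event with no OS time.

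**The case against.** The strongest reply is that the protocol forbids the exclusion. Section 6.5 keeps every randomised patient, section 6.6 requires follow-up whether or not treatment stops early, and the letter to general practitioners of current participants repeats the intention-to-treat commitment for women who decline the switch. Only the safety set is limited to dosed patients. This stands. A reader might infer from section 14.2 that the protocol plans a treated-patients OS analysis; the documents do not support that. They contain a contradiction, and the intention-to-treat rule shows which way it should be resolved. It remains a contradiction, because section 14.2 still gives no start date for the patients whom section 6.5 keeps.

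A second reply is that the effect is likely to be small. Patients have consented and are due to start within days, so large non-start is not to be expected. The counts in the working rest on assumed rates, and nothing in the documents shows that non-start differs by arm or relates to prognosis. This stands too. Bias through differential non-start is a possible mechanism, not a demonstrated one.

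Two further readings go too far.

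- A reader might take the 'post-treatment' wording in sections 15.4.1 and 15.4.2 as a third time origin. Section 15.4.1 ties its time point to the period before the tamoxifen arm switches, so it cannot mean after treatment ends. Sections 5 and 14.1 time DFS from randomisation, and sections 15.2 and 15.6 count the 2.75 years from there. This is loose wording settled by the formal definition.
- A reader might call OS the main secondary endpoint. The study summary lists it first, but section 5 lists DFS at 10 years first and section 15.4.3 does not rank them.

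**Conclusion.** Section 14.2 is wrong as written and should be fixed. It leaves OS undefined for never-dosed patients, gives no OS time to a death before the first dose, and cannot be reconciled with section 6.5 or with the origin used for the other time-to-event endpoints.

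The numerical consequence is unknown. What matters is the never-started group, and its size and balance between arms cannot be bounded from the protocol. The time shift for treated patients is negligible if the start window is kept. Since OS is a secondary endpoint without stated power, and the 723-event DFS analysis does not depend on it, this does not threaten the main conclusions of the trial.

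The statistical analysis plan was not available. It may use the right origin, but the protocol definition would still need correcting, because it states a rule that conflicts with the protocol's own analysis principle.

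**What to change.** In section 14.2, define OS as the time from randomisation to death from any cause in all randomised patients, with those not known to have died censored at the date last known alive.

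As a minor editorial alignment, replace 'post-treatment' with 'from randomisation' in sections 15.4.1 and 15.4.2.

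The cost is three wording changes. Section 8.1 already has the randomisation date recorded for every patient, so no new data or patients are needed and no stated power or event target changes. Section 15.1 says that each country has its own protocol and that the data are pooled centrally, so the same definition should be checked in the other country protocols. The edits need the amendment route in section 17.3 and can go with the next amendment.
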